Note: Individuals who receive 3 doses of the vaccine can contribute person-time to both the dose 3 exposed and dose 3 unexposed cohorts. Individuals in the dose 3 unexposed cohort may contribute person-time to the dose 3 exposed cohort if they subsequently receive a third dose of the Pfizer-BioNTech original monovalent COVID-19 Vaccine. Conversely, individuals in the dose 3 exposed cohort may be eligible for the dose 3 unexposed cohort before they receive a third dose of Pfizer-BioNTech original monovalent COVID-19 Vaccine.

8.2.3.3. Analysis of small size for gestational age and major congenital malformations in pregnant women

Cohort definitions for analyses of small size for gestational age and major congenital malformations in pregnant women are presented in Table 6. For these analyses, separate cohorts of the following will be formed: (1) pregnant women exposed to at least a first, second, or third dose of Pfizer-BioNTech original monovalent COVID-19 Vaccine during the exposure window (as defined in Table 3) and (2) pregnant women not exposed to any COVID-19 vaccine during the exposure window (as defined in Table 3).

Table 6.Cohort definitions for analysis of small size for gestational age and major
congenital malformations in pregnant women

Cohort	Inclusion criteria	Index date	Exclusion criteria
Exposed	Record of at least a first, second, or third dose (as an additional dose in a primary series or as a booster dose) of Pfizer-BioNTech original monovalent COVID-19 Vaccine during the exposure window (as defined in Table 3)	Estimated pregnancy start	Record of another brand of COVID-19 vaccine other than Pfizer-BioNTech original monovalent COVID-19 Vaccine during the exposure window No record of Pfizer- BioNTech original monovalent COVID-19 Vaccine during the exposure window
Unexposed	No record of any COVID-19 vaccine during the exposure window (as defined in Table 3), individually matched to women in the exposed cohort on maternal age and pregnancy start	Estimated pregnancy start	Record of any COVID-19 vaccine during the exposure window

COVID-19 = coronavirus disease 2019.

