Cohort definitions for third dose analyses of the general population, immunocompromised individuals, and individuals with a history of COVID-19 are described in Table 2. To be eligible, individuals older than 1 year of age must be enrolled for at least 12 months before the index date or from the earliest date that they were eligible to receive the vaccine until the index date—whichever period is longer. Depending on whether data on vaccine dose number are recorded in the data sources, additional enrollment may be required from the beginning of authorization of the Pfizer-BioNTech original monovalent COVID-19 Vaccine (i.e., 11 December 2020) to enable dose number identification. The feasibility of determining dose number based on vaccine codes will be confirmed during the monitoring phase of the study, and all eligibility criteria will be fully documented in the SAP.

Table 2.Cohort definitions for third dose analyses of the general population,
immunocompromised individuals, and individuals with a history of
COVID-19

Cohort	Inclusion criteria	Index date	Exclusion criteria
Dose 3 exposed	Receipt of 3 doses of Pfizer- BioNTech original monovalent COVID-19 Vaccine, with the third dose received more than 2 months after the second dose The third dose may be either an additional dose in a primary series or a booster dose.	Date of third dose of Pfizer-BioNTech original monovalent COVID-19 Vaccine	Record of any COVID-19 vaccine other than Pfizer- BioNTech original monovalent COVID-19 Vaccine before the index date

Table 2.Cohort definitions for third dose analyses of the general population,
immunocompromised individuals, and individuals with a history of
COVID-19

Cohort	Inclusion criteria	Index date	Exclusion criteria

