Dose 3 unexposed	 As of the index date, receipt of 2 doses in a primary series of Pfizer-BioNTech original monovalent COVID-19 Vaccine, with no receipt of a third dose of any COVID-19 vaccine Individually matched to individuals in the dose 3 exposed cohort (in at least a ratio of 1:1) on time-specific propensity score (which is described in Section 8.7.2.3.1), age, sex, state of residence (if feasible, or broader geographic region if not feasible), calendar time, and time since receipt of dose 2 	Randomly selected date in a period within close temporal proximity to the date of receipt of dose 3 in corresponding exposed individuals (e.g., within the same calendar month)	Record of any COVID- 19 vaccine other than Pfizer-BioNTech original monovalent COVID-19 Vaccine before the index date

COVID-19 = coronavirus disease 2019.

Individuals who receive 3 doses of the Pfizer-BioNTech original monovalent COVID-19 Vaccine can contribute non-overlapping person-time to both the dose 3 exposed and dose 3 unexposed cohorts. Individuals in the dose 3 unexposed cohort may also contribute persontime to the dose 3 exposed cohort if they subsequently receive a third dose of the Pfizer-BioNTech original monovalent COVID-19 Vaccine more than 2 months after the second dose. Conversely, individuals in the dose 3 cohort may be eligible for inclusion in the dose 3 unexposed cohort before they receive a third dose of Pfizer-BioNTech original monovalent COVID-19 Vaccine.

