CT24-WI-GL02-RF02 3.0 Non-Interventional Study Protocol Template For Secondary Data Collection Study 20-May-2021 Page 55 of 120 events. In addition to meeting criteria described in Table 2, individuals must also meet criteria in Table 4 to be included in the exposed/unexposed cohorts.

Cohort	Inclusion criteria	Index date	Exclusion criteria
Dose 1 exposed	Record of a first dose of Pfizer- BioNTech original monovalent COVID-19 Vaccine during the exposure window ^b	Date of first dose	Record of any COVID-19 vaccine other than Pfizer- BioNTech original monovalent COVID-19 Vaccine before the index date (or during the exposure window before the index date in analyses of spontaneous abortion, stillbirth, and preterm birth)
Dose 2 exposed	 Record of a second dose of Pfizer-BioNTech original monovalent COVID-19 Vaccine during the exposure window For analysis of general safety events, the first dose is not required to have been administered during the exposure window For analysis of spontaneous abortion, stillbirth, and preterm birth, if the first dose is administered before the exposure window, the pregnancy will NOT be eligible for dose 1 exposed cohort analysis but will be eligible for dose 2 exposed cohort analysis 	Date of second dose	Record of any COVID-19 vaccine other than Pfizer- BioNTech original monovalent COVID-19 Vaccine before the index date (or during the exposure window before the index date in analyses of spontaneous abortion, stillbirth, and preterm birth)

Table 4.Cohort definitions for primary series analyses of general safety events,
spontaneous abortion, stillbirth, and preterm birth in pregnant women^a

Table 4.	Cohort definitions for primary series analyses of general safety events,
	spontaneous abortion, stillbirth, and preterm birth in pregnant women ^a

Cohort	Inclusion criteria	Index date	Exclusion criteria

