Dose 3 exposed	 Record of a third dose (either as an additional dose in a primary series or as a booster dose) of Pfizer-BioNTech original monovalent COVID-19 Vaccine during the exposure window For analyses of general safety events, the first and second dose are not required to have been administered during the exposure window For analyses of spontaneous abortion, stillbirth, and preterm birth, the first and/or second doses may be administered before the exposure window but only the third dose will be eligible for the dose 3 cohort 	Date of third dose	Record of any COVID-19 vaccine other than Pfizer- BioNTech original monovalent COVID-19 Vaccine before the index date (or during the exposure window before the index date in analyses of spontaneous abortion, stillbirth, and preterm birth)
Dose 1 unexposed	 No record of any COVID-19 vaccine as of the index date (or no record of any COVID-19 vaccine during the exposure window before the index date in analyses of spontaneous abortion, stillbirth, and preterm birth) Individually matched to women in dose 1 cohort on maternal age and pregnancy start date and US state (if feasible) 	Equivalent of the gestational age (in days) at the time of the of the dose 1 exposed individual's index datec	Record of any COVID-19 vaccine as of the index date (or during the exposure window before the index date in analyses of spontaneous abortion, stillbirth, and preterm birth)
Dose 2 unexposed	Same criteria as the dose 1 unexposed cohort, but matched individually to women in the dose 2 exposed cohort	Equivalent of the gestational age (in days) at the time of the dose 2 exposed individual's index date ^c	Same criteria as those for the dose 1 unexposed cohort

Table 4.	Cohort definitions for primary series analyses of general safety events,
	spontaneous abortion, stillbirth, and preterm birth in pregnant women ^a

Cohort	Inclusion criteria	Index date	Exclusion criteria
Dose 3 unexposed	Same criteria as those for the dose 1 unexposed cohort, but matched individually to women in the dose 3 exposed cohort	Equivalent of the gestational age (in days) at the time of the dose 3 exposed individual's index date ^c	Same criteria as those for the dose 1 unexposed cohort

COVID-19 = coronavirus disease 2019; FU = follow-up.

a. Safety events of interest listed in Table 8 in Section 8.3.2.1.

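### Section 8.2.3.1 makes Table 2, the third-dose table for non-pregnant populations, an entry condition for the pregnant primary-series cohorts, which contradicts Table 4

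*Protocol*

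**What the plan says.** Section 8.2.3.1 covers doses 1 and 2 in pregnant women, and dose 3 only when given within 2 months of dose 2. It presents its cohorts in Table 4 and then adds a joint condition: "In addition to meeting criteria described in Table 2, individuals must also meet criteria in Table 4 to be included in the exposed/unexposed cohorts".

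Table 2 belongs to Section 8.2.2.2, which says: "Cohort definitions for third dose analyses of the general population, immunocompromised individuals, and individuals with a history of COVID-19 are described in Table 2". Its exposed row requires "Receipt of 3 doses of Pfizer- BioNTech original monovalent COVID-19 Vaccine, with the third dose received more than 2 months after the second dose", with the third-dose date as index date. Its comparator row requires "As of the index date, receipt of 2 doses in a primary series of Pfizer-BioNTech original monovalent COVID-19 Vaccine" and rules out anyone who by then has had a further dose of whatever brand.

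Table 4 defines dose 1 exposure as "Record of a first dose of Pfizer- BioNTech original monovalent COVID-19 Vaccine during the exposure window", with the first-dose date as index date. Its dose 1 comparator has "No record of any COVID-19 vaccine as of the index date". For spontaneous abortion, stillbirth and preterm birth, that comparator rule is limited to the exposure window before the index date. The dose 2 and dose 3 comparators take over the dose 1 criteria.

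**The concern.** The sentence is an eligibility rule for both exposed and unexposed women, and it joins two tables written for different questions. Table 2 asks whether a third dose adds risk among people who already have two. Table 4 asks whether a primary-series dose adds risk compared with no vaccination.

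These cohorts serve primary objective 1 in the subgroup of pregnant women (Section 7). Under Section 8.6.3 the coordinating center writes the programs and the data research partners run them, so a misapplied criterion would be repeated in all five data sources.

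**Working it through.** The plan gives no figure to reproduce, so the check is logical. Describe each woman at her index date by (b, w), where b is the number of Pfizer-BioNTech doses before the exposure window and w is the number inside the window before the index date. With b + w from 0 to 3 there are ten histories.

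Table 2, either cohort: b + w = 2. In the exposed cohort the index dose is the third; in the comparator there is no third dose. The histories are (2,0), (1,1) and (0,2).

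Table 4 compared with Table 2:

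| Cohort in Table 4 | Histories allowed by Table 4 | Also meeting Table 2 |
|---|---|---|
| Dose 1, 2, 3 unexposed, general safety events | b + w = 0: (0,0) | none |
| Dose 1, 2, 3 unexposed, spontaneous abortion, stillbirth, preterm birth | w = 0: (0,0), (1,0), (2,0), (3,0) | (2,0) only |
| Dose 1 exposed | b + w = 0: (0,0) | none |
| Dose 2 exposed | b + w = 1: (0,1), (1,0) | none |
| Dose 3 exposed | b + w = 2, third dose within 2 months of the second | none: Table 2 requires more than 2 months |

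Three details matter.

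1. For dose 1 and dose 2 exposed, the index dates conflict. One date would have to be both the first-dose (or second-dose) date and the third-dose date.

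2. For dose 3 exposed, the 2-month limit is not in the Table 4 row. It is in the paragraph that introduces the table and again in Section 8.7.2.3.2.1. If the row were read without that limit, the women admitted would be those with late third doses, whose analysis is in Section 8.2.3.2 and Table 5.

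3. For the three pregnancy outcomes, the (2,0) women pass the dose-history criteria as comparators, but the dose 1 exposed row holds nobody to match them to. Only footnote b of Table 4 leaves a residue, because it lets a later dose that is the first inside the window count as dose 1. With (2,0) on both sides, that is a third-dose comparison rather than a primary-series one.

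With Table 2 removed, the general-safety comparators are the (0,0) women, dose 1 exposure is a true first dose, and the pregnancy-outcome comparators are all women with w = 0. No cohort is then empty by definition, and the never-vaccinated comparators of Section 8.7.2.3.2.1 are admitted.

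On which table was meant, the document does not say, but the pregnancy sections point to Table 3. Section 8.2.3 places eligible populations and exposure windows there. Sections 8.2.3.2 and 8.2.3.3 both cite it for the same purpose, and Table 4 uses an exposure window that Table 3 defines.

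Table 1 would bring new conflicts. It bars any earlier COVID-19 vaccine for dose 1 exposed and all unexposed cohorts, whereas Table 4 limits the unexposed rule to the window for the three pregnancy outcomes. It also matches on propensity score. Section 8.7.2.3.2.1 matches on pregnancy start, state and maternal age, then uses the score by weighting or stratification.

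**The case against.** The best reply is that this is a slip that any careful reader would correct. The same section presents its cohorts in Table 4, Section 8.2.3 points to Table 3, and Section 8.7.2.3.2.1 states the unvaccinated comparator. A programmer who applied Table 2 would get empty cohorts and notice. Most of this stands, and it is why the point is a correction and not a flaw in the design. It does not remove the contradiction, because the sentence is current text that sets a specific condition.

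A reader might infer more than the documents support:

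- That dose 1 exposure would be restricted to women who later had a third dose, and so would condition on the future. It would not: Table 2 fixes the index date at the third dose and Table 4 at the first, so the combined set is empty, not selectively reduced.
- That no comparator survives for any outcome. This is strict only for general safety events. For the three pregnancy outcomes the (2,0) women pass, although they are not the intended comparators.
- That the choice between Table 1 and Table 3 settles whether women vaccinated before the window may enter. Table 4 already addresses this for the pregnancy outcomes, and Section 8.2.3 says that women vaccinated outside the window may contribute unexposed person-time. Table 1 is also titled for the non-pregnant groups only.

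**Conclusion.** The point holds as an internal cross-reference error in an operative eligibility rule. Applied literally, all three exposed rows are empty, no unexposed woman qualifies for general safety events, and the never-vaccinated comparator is excluded for every outcome in Section 8.2.3.1.

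This rests on reading the sentence as a joint requirement, which its wording says, and on applying each table's own index date together with the section's 2-month limit. It does not imply that the study will run on empty cohorts, since the intent is largely recoverable. That Table 3 was intended is the best-supported reading, but it is an inference.

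**What to change.** In Section 8.2.3.1, replace the reference to Table 2 with Table 3, so that a woman must meet the eligible population and exposure window in Table 3 and the cohort criteria in Table 4. Deleting the Table 2 clause would work equally well, because Section 8.2.3 already applies Table 3. The sponsor should confirm which table was meant. Do not substitute Table 1.

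The cost is one corrected reference before cohort programming, with no change to data, design or analysis.

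A separate matter remains after this fix. For a first dose before the window and a second inside it, in the pregnancy-outcome analyses, the dose 2 row of Table 4 assigns the woman to the dose 2 cohort and not to dose 1, while footnote b says her second dose could contribute to the dose 1 cohort. The sponsor should reconcile these in the same revision.
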